2 OBJECTIVES

2.1 Primary objective

The primary objective of study BPR-CP-101 is to assess the pharmacokinetics (PK) of a single oral dose of pitavastatin, administered without and with intravenous (iv) ceftobiprole in healthy subjects.

2.2 Secondary objectives

The secondary objectives are:

- To assess the pharmacodynamic (PD) effect of iv ceftobiprole on the diurnal plasma level profile of coproporphyrin I (CP-I) in healthy subjects
- To describe the systemic exposure of iv ceftobiprole without and with oral administration of pitavastatin in healthy subjects
- To assess the single-dose plasma PK of the pitavastatin metabolite, pitavastatin lactone, after a single oral dose of pitavastatin, administered without and with iv ceftobiprole in healthy subjects
- To assess the safety and tolerability of ceftobiprole without and with administration of a single oral dose of pitavastatin in healthy subjects.

3 INVESTIGATIONAL PLAN

3.1 Overall study design

3.1.1 Brief summary

This is a Phase 1, single-center, open-label, non-randomized, fixed-sequence, drug-drug interaction study in healthy male or female subjects to assess if there is an inhibitory effect of ceftobiprole on the hepatic OATP1B activity. Pitavastatin is used as an OATP1B substrate in this study. The PK of oral pitavastatin is assessed when administered alone and when administered together with iv ceftobiprole in a study design including two treatment periods. In addition, the PD effect of repeated doses of iv ceftobiprole on the diurnal plasma

levels of CP-I is assessed in this study as CP-I is an endogenous biomarker for hepatic OATPB1 activity.

An overview of the study design is provided in protocol Section 3.1. The schedule of assessments and procedures for the different periods are provided in protocol Table 1.

3.1.2 Number of subjects

Twelve subjects will be enrolled in the study. If a subject does not complete the study for a reason not related to the study drug, the early-termination subject may be replaced.

3.1.3 Treatments

The following treatments are planned to be administered in two periods:

- Period 1 (from Day -1 to Day 3): pitavastatin single dose
 - Day 1: a single oral dose of 2 mg pitavastatin is administered in the morning under fasted conditions.
- Period 2 (from Day 4 to Day 8): pitavastatin single dose + ceftobiprole every 8 hours (q8h)
 - Day 4 to Day 7: 500 mg ceftobiprole (as the prodrug ceftobiprole medocaryl sodium) is administered as a 2-hour iv dose q8h under fasted conditions in the morning, and irrespective of timing of food intake further on the day.
 - Day 6: a single oral dose of 2 mg pitavastatin is coadministered with ceftobiprole 30 minutes prior to the end of the first iv dose of 500 mg ceftobiprole under fasted conditions.

3.2 Study endpoints

3.2.1 Primary endpoints

The primary endpoints are the plasma PK parameters of pitavastatin including C_{max} , t_{max} , k_{el} , $t_{1/2}$, AUC_{0-t} , AUC_{0-inf} , CL/F , and V_z/F , as appropriate.

3.2.2 Secondary endpoints

The secondary endpoints are:

- Plasma exposure parameters of CP-I, including $AUEC_{0-25.5h}$, C_{max} , t_{max} , C_{trough} , and $C_{25.5h}$.
- Plasma exposure parameters of ceftobiprole, including C_{trough} , C_{max} , t_{max} , k_{el} , $t_{1/2}$, AUC_{0-8h} , CL , and V_z , as appropriate.
- Plasma PK parameters of pitavastatin lactone including C_{max} , t_{max} , k_{el} , $t_{1/2}$, AUC_{0-t} , AUC_{0-inf} , as appropriate.
- Ratios of C_{max} , AUC_{0-t} , and AUC_{0-inf} of pitavastatin lactone over parent drug.
- Type, frequency, severity, timing, and relationship to study drug of any adverse events (AEs).

- Abnormalities and changes from baseline in clinical laboratory, vital signs, and 12-lead electrocardiogram (ECG) parameters, as appropriate.

4 GENERAL STATISTICAL CONSIDERATIONS

Summary outputs will be presented overall, except adverse events that will be summarized by period (see Section 9.1 for details) and overall. No formal hypothesis testing will be performed. Continuous data, unless otherwise specified, will be described using descriptive statistics (n, mean, standard deviation [SD], median, minimum, and maximum). Categorical data will be described using the subject count and percentage in each category. Non-zero percentages will be rounded to one decimal place, except 100%, which will be displayed without any decimal places. For the summary statistics of all numerical variables unless otherwise specified, minimum and maximum will be displayed to the same level of precision as reported, up to a maximum of three decimal places. Mean and median will be displayed to one level of precision greater than the data collected, up to a maximum of three decimal places. Standard deviation will be displayed to two levels of precision greater than the data collected, up to a maximum of three decimal places.

When count data are presented, the percentage will be suppressed when the count is zero, to draw attention to the non-zero counts. A row denoted 'Missing' will be included in count tabulations where specified in the table shells, to account for dropouts and missing values. The denominator for all percentages will be the number of subjects in the population of interest, unless otherwise specified.

All data will be displayed in listings sorted by subject ID and treatment periods, when applicable.

4.1 Sample size justification

The sample size has been based on the desire to obtain adequate PK, PD, safety, and tolerability data to achieve the objectives of the study.

The intended sample size of 12 subjects is considered adequate to fully address the primary objective of the study, given the precedence of earlier studies with pitavastatin as probe substrate.

4.2 Analysis sets

4.2.1 Safety set

The safety set consists of all enrolled subjects who have received at least one dose of study drug.

4.2.2 Pharmacokinetic set

The PK set consists of all subjects who received at least one dose of study drug and provided sufficient bioanalytical assessment results to calculate reliable estimates of the PK parameters.

4.2.3 Pharmacodynamic set

The PD set consists of all subjects for whom the PD data are considered to be sufficient and interpretable.

4.3 Other important considerations

4.3.1 Definition of baseline

Unless otherwise specified, baseline is defined as the last non-missing assessment prior to the first study drug administration. Both scheduled and unscheduled visits and assessments will be used in determining baseline.

4.3.2 Study day calculation and visit windows

Visit windowing approaches will not be used for this study, and visit based summaries will include scheduled assessments only.

The following conventions will be used to calculate analysis study day:

- Day 1 is the day of first study drug administration. Day -1 is the day before Day 1. No Day 0 is defined for this study.
- Prior to Day 1, the algorithm is:
 $\text{Study Day} = \text{visit/examination date} - \text{date of first study drug administration}$
- For Day 1 and subsequent days, the algorithm is:
 $\text{Study Day} = \text{visit/examination date} - \text{date of first study drug administration} + 1.$

Summary data such as AEs will not be reported by visit. Tables that report abnormalities (e.g., laboratory shift tables) will include all assessments.

4.3.3 Missing and partial data

The following rules for missing data will be followed:

- AE date imputations will follow the rules described in [Appendix 1](#).
- The causality assessment for AEs should not be missing and will be queried for a value. AEs with missing causality will be considered related to study drug.

4.3.4 Duration (e.g., for adverse events)

If date and time are collected, then duration is calculated as event end date and time minus event onset date and time. Duration will be displayed as days and fractions of days, or as hours and fractions of hours, as appropriate.

If only the date is collected, then the duration in days is calculated as event end date minus event onset date + 1.

4.3.5 Elapsed actual time

For PK blood sampling, elapsed actual time in hours is the number of hours elapsed from date and time of study drug administration on related day (Day 1 or Day 6 for pitavastatin PK and CP-I, Day 5 and Day 6 for ceftobiprole PK). This time is derived from actual dates and times recorded in the eCRF.

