- i. Blood sampling for PK of pitavastatin and its metabolite pitavastatin lactone in plasma on Day 1 (before pitavastatin dosing and 0.25, 0.5, 0.75, 1, 1.5, 2, 2.5, 3, 4, 6, 8, 10, and 12 hours after pitavastatin dosing), Day 2 (24 and 36 hours after pitavastatin dosing), and Day 3 (48 hours after pitavastatin dosing), and on Day 6 (before pitavastatin dosing and 0.25, 0.5, 0.75, 1, 1.5, 2, 2.5, 3, 4, 6, 8, 10, and 12 hours after pitavastatin dosing), Day 7 (24 hours and 36 after pitavastatin dosing), and Day 8 (48 hours after pitavastatin dosing). Note: [Table 2](#) provides the PK sampling time points relative to Day 1 pitavastatin administration.
- j. Blood sampling for ceftobiprole PK in plasma on Day 4: predose and 2 hours (immediately after infusion stop) after start of the first infusion on Day 4; on Day 5: predose and 1, 2 (immediately after infusion stop), 4, 6, and 8 hours (predose prior to the second infusion on Day 5) after start of the first infusion on Day 5; on Day 6 (predose), and 1, 2 (immediately after infusion stop), 4, 6, and 8 hours (predose for the second infusion on Day 6) after start of the first infusion on Day 6, and on Day 7 (predose, prior to the first infusion on Day 7). Note: [Table 2](#) provides the PK sampling time points relative to Day 1 pitavastatin administration.
- k. Blood sampling for OATP1B activity marker CP-I in plasma: on Day 5 prior to the start of the first ceftobiprole infusion in the morning, at 2, 4, 6, and 8 hours after the start of the first ceftobiprole infusion on Day 5 (8-hour sample just prior to the start of the second ceftobiprole infusion), at 16 hours after the start of the first ceftobiprole infusion on Day 5 (just prior to the start of the third ceftobiprole infusion on Day 5), and prior to pitavastatin dosing on Day 6 (approximately 25.5 hours after the start of the first ceftobiprole infusion on Day 5) (total of 7 samples). On Day -1 and Day 1, a total of 7 samples will be taken at the corresponding clock times as are planned for Day 5 and Day 6. Note: [Table 2](#) provides the sampling time points relative to Day 1 pitavastatin administration.

**Table 2 Detailed Schedule of Administration of Pitavastatin and Ceftobiprole, and Assessments With Time Points Relative to Day 1 Pitavastatin Dosing**

Day	Time Point With Day 1 Pitavastatin Dosing as Baseline (hours)	Dose	PK of Pitavastatin and Metabolite	Ceftobiprole PK	CP-I Blood Sampling	12-Lead ECG	Vital Signs
Screening						X	X
-2						X	X

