-1	-25.5				X		X
	-23.5				X		
	-21.5				X		
	-19.5				X		
	-17.5				X		
	-9.5				X		
1	Predose Pitavastatin		X		X		X
	0	Day 1 Pitavastatin Dosing					
	0.25		X				
	0.5		X				
	0.75		X				
	1		X				
	1.5		X				
	2		X				X
	2.5		X				
	3		X				
	4		X				
	6		X				
	8		X				
	10		X				
	12		X				
2	24		X				X
	36		X				
3	48		X				X
4	Predose Ceftobiprole			X			X
	70.5	Start Day 4 First Ceftobiprole Infusion					
	72.5	End Day 4 First Ceftobiprole Infusion		X (Immediately After Stopping Day 4 First Ceftobiprole Infusion)		X (Prior to Stopping Day 4 First Ceftobiprole Infusion)	X (Prior to Stopping Day 4 First Ceftobiprole Infusion)
	78.5	Start Day 4 Second Ceftobiprole Infusion					

Day	Time Point With Day 1 Pitavastatin Dosing as Baseline (hours)	Dose	PK of Pitavastatin and Metabolite	Ceftobiprole PK	CP-I Bood Sampling	12-Lead ECG	Vital Signs
	80.5	End Day 4 Second Ceftobiprole Infusion					
	86.5	Start Day 4 Third Ceftobiprole Infusion					
	88.5	End Day 4 Third Ceftobiprole Infusion					
5	Predose Ceftobiprole			X	X (Prior to Starting Day 5 First Ceftobiprole Infusion)		X (Prior to Starting Day 5 First Ceftobiprole Infusion)
	94.5	Start Day 5 First Ceftobiprole Infusion					
	95.5			X			
	96.5	End Day 5 First Ceftobiprole Infusion		X (Immediately After Stopping Day 5 First Ceftobiprole Infusion)	X		
	98.5			X	X		
	100.5			X	X		
	Predose Ceftobiprole			X (Prior to Starting Day 5 Second Ceftobiprole Infusion)	X (Prior to Starting Day 5 Second Ceftobiprole Infusion)		
	102.5	Start Day 5 Second Ceftobiprole Infusion					
	104.5	End Day 5 Second Ceftobiprole Infusion					
	Predose Ceftobiprole				X (Prior to Starting Day 5 Third Ceftobiprole Infusion)		
	110.5	Start Day 5 Third Ceftobiprole Infusion					

Day	Time Point With Day 1 Pitavastatin Dosing as Baseline (hours)	Dose	PK of Pitavastatin and Metabolite	Ceftobiprole PK	CP-I Blood Sampling	12-Lead ECG	Vital Signs
	112.5	End Day 5 Third Ceftobiprole Infusion					
6	Predose Ceftobiprole			X (Prior to Starting Day 6 First Ceftobiprole Infusion)			X (Prior to Starting Day 6 First Ceftobiprole Infusion)
	118.5	Start Day 6 First Ceftobiprole Infusion					
	119.5			X			
	Predose Pitavastatin		X		X (Prior to Day 6 Pitavastatin Dosing)		
	120	Day 6 Pitavastatin Dosing					
	120.25		X				
	120.5	End Day 6 First Ceftobiprole Infusion	X	X (Immediately After Stopping Day 6 First Ceftobiprole Infusion)		X (Prior to Stopping Day 6 First Ceftobiprole Infusion)	X (Prior to Stopping Day 6 First Ceftobiprole Infusion)

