#### **3.5.2.1 Timing of Assessments**

For pitavastatin PK, predose samples will be obtained between waking up and dosing. Postdose samples up to 20 minutes postdose will be obtained with a time window of ±1 minute. Thereafter, postdose samples will be obtained with time margins of ±5% of the time that has passed since dosing.

For ceftobiprole PK, samples prior to the first infusion of a day will be obtained between waking up and the start of the iv infusion. For predose (trough) samples during multiple dosing, a 5% time

window since the last dose is allowed, but the sample must be taken before the next dose. Postdose samples up to 20 minutes after the start of the iv infusion will be obtained with a time window of  $\pm 1$  minute. Thereafter, postdose samples will be obtained with time margins of  $\pm 5\%$  of the time that has passed since the start of the iv infusion.

For CP-I diurnal profiling on Days -1 to 1 and on Days 5 to 6, samples will be obtained within margins of  $\pm 15$  minutes. On Day 5, the first sample will be obtained prior to the start of the iv infusion with ceftobiprole. On Days 1 and 6, the last CP-I sample will be collected prior to pitavastatin dosing.

For safety assessments, predose assessments will be performed between waking up and dosing / the start of the iv infusion. For safety assessments up to 2.5 hours postdose/after the start of the iv infusion, a time window of  $\pm 15$  minutes is allowed. Thereafter, serial postdose assessments (e.g., multiple assessments within any given day) must be performed with time margins of  $\pm 10\%$  of the time that has passed since (last) dosing/the start of the iv infusion.

When assessments are planned for the same scheme time, the order of the assessments should be arranged in such a way that PK and PD blood sampling will be done after the ECG and vital signs recordings have been conducted, with PK blood sampling exactly on time.

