**Table 4 Pharmacodynamic Parameters**

Parameter	Description
$C_{max}$	Maximum observed plasma level
$t_{max}$	Time to attain maximum observed plasma level
$C_{trough}$	Trough plasma level
$C_{25.5h}$	Plasma level at 25.5 hours after the start of the first ceftobiprole infusion on Day 5 (prior to pitavastatin dosing on Day 6) or at the corresponding clock time on Day 1
$AUEC_{0-25.5h}$	Area under the plasma level-time curve up to time 25.5 hours after the start of the first ceftobiprole infusion on Day 5 (prior to pitavastatin dosing on Day 6) or at the corresponding clock time on Day 1

In addition,  $C_{max}$ ,  $AUEC_{0-25.5h}$ ,  $C_{trough}$  and  $C_{25.5h}$  ratio between Days 5 to 6/Days -1 to 1, and shift (if any) of  $t_{max}$  on Days 5 to 6 versus Days -1 to 1 will be calculated.

The PD parameters and their statistical evaluation will be included in the CSR for this study.

All data will be summarized using descriptive statistics and will be listed and summarized in tabular and/or graphical form.

Statistical analysis will be performed on PD parameters to compare baseline CP-I plasma concentrations to CP-I plasma concentrations after multiple doses of ceftobiprole. A mixed-effects model with subject as a random effect and treatment as a fixed effect will be performed on the following natural logarithm (ln)-transformed PK parameters of CP-I:  $C_{max}$ , and  $AUEC_{0-25.5h}$ . The ratio of geometric least squares means, expressed as test (during administration of ceftobiprole)/reference (CP-I baseline), and corresponding 90% CIs will be presented.

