8.2 PK parameters

Individual PK parameters will be estimated using non-compartmental methods with WinNonlin[®].

The plasma PK parameters will be estimated from the concentration-time profiles. In estimating the PK parameters, BLQ values at the beginning of the profile will be set to zero. BLQ values that occur after the first quantifiable point will be considered missing. Values that are embedded between BLQs, or quantifiable values occurring after two or more BLQs, will be set to missing at the discretion of the pharmacokineticist and in agreement with the Sponsor. Actual sampling times, rather than scheduled sampling times, will be used in all computations involving sampling times. If the actual time or dose time is missing, the scheduled time may be substituted in order to calculate the PK parameter.

The PK parameters to be determined or calculated using noncompartmental analysis from the plasma concentration-time data are:

- For pitavastatin and pitavastatin lactone on Day 1 and Day 6: C_{max} , t_{max} , k_{el} , $t_{1/2}$, AUC_{0-t} , AUC_{0-inf} , AUC_{extrap} , adjusted R-squared, CL/F (pitavastatin only), V_z/F (pitavastatin only), as appropriate; ratios of C_{max} , AUC_{0-t} , and AUC_{0-inf} of pitavastatin lactone over parent drug; AUC and C_{max} ratio Day 6/Day 1 for pitavastatin and pitavastatin lactone.
- For ceftobiprole on Day 5 and Day 6: C_{trough} , C_{max} , t_{max} , k_{el} , $t_{1/2}$, AUC_{0-8h} , AUC_{extrap} , adjusted R-squared, CL, and V_z , as appropriate.

Following administration, C_{max} and t_{max} will be obtained directly from the experimental observations. If multiple maxima occur at equal concentrations, the first temporal value will be taken. AUC will be calculated using the linear up/log down trapezoidal rule, using actual elapsed time since the start of administration. The number of data points included in the regression of k_{el} and $t_{1/2}$ after single dose will be determined by visual inspection, but a minimum of 3 data points in the terminal phase, excluding C_{max} , will be required to estimate k_{el} . The k_{el} values (and consequently $t_{1/2}$, CL/F, V_z/F , AUC_{0-inf}) will be considered unreliable estimates if the period of time is over which an individual k_{el} was estimated is less than twice the resultant $t_{1/2}$ or if the adjusted coefficient of determination R-squared is less than or equal to 0.75.

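### SAP 4.3.5 times CP-I from the Day 1 and Day 6 dose, although both CP-I profiles end before the pitavastatin dose and protocol Table 4 counts from the first Day 5 infusion

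*SAP*

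**What the plan says.** SAP 4.3.5 defines elapsed actual time as hours since study drug administration on the related day, and lists the days as "Day 1 or Day 6 for pitavastatin PK and CP-I, Day 5 and Day 6 for ceftobiprole PK". CP-I is thus grouped with pitavastatin.

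SAP 8.3 gives CP-I no time origin of its own. It says that the CP-I parameters are estimated by methods similar to those for PK. Those methods, in SAP 8.2, compute area by linear up/log down trapezoids "using actual elapsed time since the start of administration". SAP 11 declares no change from the protocol's analyses.

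The protocol places the samples differently. Section 3.5.2.1 states: "On Days 1 and 6, the last CP-I sample will be collected prior to pitavastatin dosing". Footnote k of Table 1 describes the Days 5 to 6 profile as one sample before the first Day 5 infusion, then samples at 2, 4, 6, 8 and 16 h after its start, and a last one about 25.5 h after it. For the baseline profile, "a total of 7 samples will be taken at the corresponding clock times as are planned for Day 5 and Day 6". Protocol Table 4 defines AUEC0-25.5h as "Area under the plasma level-time curve up to time 25.5 hours after the start of the first ceftobiprole infusion on Day 5", with the corresponding clock time on Day 1 as the baseline equivalent. C25.5h is defined on the same scale.

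**The concern.** The SAP's time zero comes after the samples it is meant to time. A parameter defined on 0 to 25.5 h cannot be reconciled with an origin at the end of the profile, and the SAP offers no other origin for CP-I.

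CP-I exposure is a secondary endpoint and the study's endogenous marker of OATP1B activity. Three of its five listed parameters (tmax, C25.5h and AUEC0-25.5h) depend on where time starts, as do the individual CP-I plots against actual sampling time in SAP 8.1. AUEC0-25.5h is also one of the two CP-I parameters that enter the mixed model.

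The correction cannot be left to the programmer, because the right origin is not obvious in either profile. No drug is given on Day -1, so no recorded dose time marks the start of the baseline profile. On Day 6 both drugs are given, and the protocol calls both study drug.

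**Working it through.** **Inputs** (hours on the protocol Table 2 clock, where the Day 1 pitavastatin dose is 0):
- "Start Day 5 First Ceftobiprole Infusion": 94.5 h.
- Start of the first Day 6 infusion: 118.5 h.
- "Day 6 Pitavastatin Dosing": 120 h.
- CP-I sampling times: first two data columns below.

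**Step 1. Reproduce the protocol's interval.** 120 - 94.5 = 25.5 h, which matches Table 4.

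**Step 2. Apply each origin.**
- SAP 4.3.5, pitavastatin dose: t - 0 for Days -1 to 1, and t - 120 for Days 5 to 6.
- Protocol Table 4: t - (-25.5) for Days -1 to 1, and t - 94.5 for Days 5 to 6.
- Other reading of study drug on Day 6, that day's first infusion: t - 118.5 for Days 5 to 6.

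| Sample | Days -1 to 1, Table 2 | Days 5 to 6, Table 2 | SAP origin, both profiles | Protocol origin, both profiles | Day 6 first infusion as origin, Days 5 to 6 |
|---|---|---|---|---|---|
| 1 | -25.5 | 94.5 (pre-infusion) | -25.5 | 0 | -24 |
| 2 | -23.5 | 96.5 | -23.5 | 2 | -22 |
| 3 | -21.5 | 98.5 | -21.5 | 4 | -20 |
| 4 | -19.5 | 100.5 | -19.5 | 6 | -18 |
| 5 | -17.5 | 102.5 | -17.5 | 8 | -16 |
| 6 | -9.5 | 110.5 | -9.5 | 16 | -8 |
| 7 | 0 (pre-dose) | 120 (pre-dose) | just before 0 | 25.5 | 1.5 |

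Under the SAP origin, none of the 14 samples per subject lies after time 0. Under the protocol origin, all 14 lie in 0 to 25.5 h, on the same grid in both profiles.

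**Step 3. Does the shift change the modelled quantities?** Cmax uses no times. Each trapezoid uses only a time difference: Δt(c1 + c2)/2 when rising, and Δt(c1 - c2)/ln(c1/c2) when falling. A constant shift cancels from Δt. As a check, take an invented profile of 0.8, 1.1, 1.0, 0.95, 0.9, 0.85, 0.8 (arbitrary units). The pieces are 1.900 + 2.098 + 1.950 + 1.850 + 6.998 + 7.835 = 22.63, the same under both origins. Only the label of tmax moves: -23.5 h under the SAP origin, 2.0 h under the protocol origin.

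**Step 4. The planned tmax shift (Days 5 to 6 versus Days -1 to 1).** Suppose tmax is at sample 2 in both profiles, so the true shift is 0.
- Pitavastatin dose as origin in both: -23.5 - (-23.5) = 0.
- First infusion as origin on Day 6, pitavastatin dose on Day 1: -22 - (-23.5) = +1.5 h, which is spurious.

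**Step 5. Actual dosing times.** Protocol 3.4.5 allows ±15 minutes around a subject's usual dosing time on Days 1, 5 and 6. If the Day 5 infusion start and the Day 6 dose can each be off by that much, the actual gap is 25.5 ± 0.5 h, or 25.0 to 26.0 h. Subtracting 25.5 h from a pitavastatin dose time therefore does not recover the infusion start.

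**The case against.** The strongest reply is that little of substance is at stake. The SAP is to be read together with the protocol, it keeps the protocol's parameter names and its pairing of Days 5 to 6 with Days -1 to 1, and Table 4 states the origin for the infusion profile. A literal program would return negative times or an empty window, which someone would notice; it would not bias results silently. SAP 8.3 asks for similar methods, not identical ones. CP-I is secondary, the study is exploratory, and no formal hypothesis is tested.

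Most of this stands. A reader might infer that AUEC0-25.5h cannot be computed, or that the CP-I ratios and their 90% confidence intervals are lost. The documents do not support that: step 3 shows that Cmax and the area over the full profile do not depend on the origin. A reader might also infer that the tmax comparison is invalid under any reading. It is not. If both periods use the pitavastatin dose, the shift cancels apart from small differences in actual dosing time.

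The reply does not remove the contradiction. SAP 4.3.5 names CP-I and states a rule for it, so a correct analysis depends on disregarding a prespecified instruction. Table 4 does not say when the baseline profile starts on Day -1; that has to be inferred from the sampling schedule.

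**Conclusion.** SAP 4.3.5 is wrong as written for CP-I and contradicts protocol Table 4 and the sampling schedule. The size is a 25.5 h displacement of all seven nominal times in each profile.

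- **Affected if followed literally:** individual tmax is never positive, C25.5h has no sample, and the 0 to 25.5 h window for AUEC holds no data after time 0.
- **Not affected:** Cmax, and AUEC integrated over all seven samples, so the two modelled ratios hold under a constant shift.
- **Conditional risk:** the AUEC ratio is at risk if a program restricts to 0 to 25.5 h or drops pre-dose times, and the Cmax ratio if pre-dose samples are dropped. The tmax shift is biased by +1.5 h if Day 6 is timed from that day's first infusion while Day 1 is timed from pitavastatin.

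These figures use nominal Table 2 times. The primary pitavastatin analysis is untouched. Rating: should fix.

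**What to change.** Amend SAP 4.3.5 and cross-reference it in 8.3:

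1. Remove CP-I from the Day 1/Day 6 origin.
2. For Days 5 to 6, set time zero at the recorded start of the first ceftobiprole infusion on Day 5.
3. For Days -1 to 1, state one origin: the same clock time on Day -1 as that subject's recorded Day 5 infusion start. Do not offer 25.5 h before the Day 1 pitavastatin dose as an equivalent, because the two can differ when actual dosing times vary.
4. State how the first (pre-infusion) sample is assigned to time 0, and apply the same rule to the first baseline sample. SAP 8.2 calls for actual sampling times, so without a rule this sample would usually fall slightly before 0.

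The cost is a few sentences in the SAP before analysis. No sampling, data collection or protocol procedure changes.
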